Background Ulcerative colitis (UC) is a chronic inflammatory bowel disease characterized by relapsing and remitting inflammation of the colon [1]. Despite advancements in therapeutic options, including biologic agents and small molecules, many patients experience inadequate response, loss of response, or intolerance to existing treatments, especially after exposure to multiple biologics [2].

Etrasimod is a once-daily, oral selective sphingosine 1-phosphate (S1P) receptor modulator that primarily targets S1P1,4,5 with no detectable activity on S1P2,3, distinguishing it from first-generation S1P modulators associated with adverse effects [3]. By reversibly sequestering lymphocytes in lymph nodes, Etrasimod reduces peripheral immune cell trafficking to inflamed gastrointestinal tissue, thereby mitigating inflammation while maintaining immune surveillance [3,4]. This mechanism is particularly relevant for UC, as immune-mediated dysregulation contributes significantly to disease pathophysiology [4].

Recent phase 3 trials (ELEVATE UC 52 and ELEVATE UC 12) demonstrated that Etrasimod significantly improves clinical, endoscopic, and histologic outcomes in patients with moderate-to-severe UC, including those who have failed previous therapies [5]. The efficacy and tolerability of Etrasimod make it a promising oral alternative for patients requiring durable disease control without the burdens associated with parenteral biologic administration [5].

This study aims to prospectively evaluate the efficacy and safety of Etrasimod over one year in patients with moderate-to-severe UC who have previously been exposed to biologic therapies, further expanding the evidence for its real-world application and impact on symptom control, including urgency assessment through the validated Urgency Numeric Rating Scale (UNRS).

Study Design

• Type: Multicenter, Prospective, Open-Label Study

Duration: 54 weeks

- Population: Adults diagnosed with moderate-to-severe UC who have failed or are intolerant to at least one prior biologic therapy
- **Timeline:** Enrollment: July 2025 to December 2025; Treatment period: 54± 4 weeks for each participant; Data collection: as follows.

Objectives

Primary Objective:

• Evaluate the effectiveness of Etrasimod in achieving deep remission at Week 54, defined as the simultaneous presence of clinical and endoscopic remission.

Secondary Objectives:

- Assess the safety profile of Etrasimod over 54 weeks.
- Evaluate the proportion of patients achieving clinical response and biochemical response (fecal calprotectin [FC] and C-reactive protein [CRP]) at Weeks 12, 24, and 54.
- Measure improvement in patient-reported outcomes (PROs), including the urgency numeric scale (UNRS), at Weeks 12, 24, and 54.
- Assess mucosal and histological healing at Week 54 using endoscopy and biopsy.
- Evaluate changes in rectal and colonic wall thickness via ultrasound, if feasible[6].

Endpoints

Composite Endpoint:

Proportion of patients achieving deep remission at 54 ± 4 weeks, defined as: Mayo rectal bleeding subscore = 0, stool frequency subscore = 0, endoscopic subscore ≤ 1 .

Secondary Endpoints:

- Proportion of patients achieving clinical response at Weeks 12, 24, and 54, defined as
 a decrease from baseline in Mayo Clinic total score of ≥3 points and ≥30%, with a
 decrease in rectal bleeding subscore of ≥1 or an absolute rectal bleeding subscore of
 0 or 1.
- Change from baseline in PRO scores, including the urgency numeric scale (UNRS), at Weeks 12, 24, and 54.
- Proportion of patients achieving biochemical response (normalization or significant reduction in FC and CRP levels) at Weeks 12, 24, and 54.
- Safety outcomes: Incidence and severity of adverse events (AEs), serious adverse events (SAEs), and discontinuations due to AEs throughout the study.

Outcomes measurement

Primary Outcome Measures:

1. Clinical Remission at 24 and 54 ± 4 weeks

 \circ To assess the proportion of patients achieving clinical remission at 54 ± 4 weeks, defined as a modified Mayo score (MMS) with a rectal bleeding subscore of 0, stool frequency subscore of 0 or 1 with at least a 1-point reduction from baseline, and an endoscopic subscore of 0 or 1 (excluding friability).

Secondary Outcome Measures:

1. Endoscopic Remission at 54 ± 4 weeks

To determine the proportion of patients attaining endoscopic remission at 54 ± 4 weeks, defined as a Mayo endoscopic subscore of 0 or 1 (excluding friability) and UCEIS score.

2. Histologic Remission at 54 ± 4 weeks

o To evaluate histologic remission at 54 ± 4 weeks using the Nancy histological score. Remission is defined as a Nancy histological score of 0.

3. Symptomatic Remission at 12, 24 e 54 ± 4 weeks

To assess the proportion of patients achieving symptomatic remission at 12,
 24 e 54 ± 4 weeks, defined as a Mayo score with a rectal bleeding subscore of
 0 and a stool frequency subscore of 0 or 1 with at least a 1-point decrease
 from baseline.

4. Endoscopic Response at 54 ± 4 weeks

 To evaluate the proportion of patients achieving endoscopic response at 54 ± 4 weeks, defined as at least a 1-point reduction from baseline in the Mayo endoscopic subscore.

5. Clinical Response at 12, 24 and 54 ± 4 weeks

 \circ To determine the proportion of patients achieving clinical response at 12, 24 e 54 \pm 4 weeks, defined as a decrease of at least 2 points and 30% from baseline in the 9-point MMS, with either a reduction of rectal bleeding subscore by at least 1 point or an absolute rectal bleeding subscore of 0 or 1.

6. Change in Fecal Calprotectin and C-Reactive protein from Baseline to 12, 24 e 54 ± 4 weeks

 \circ Biochemical response will be defined as either normalization (FC < 150 μg/g and CRP < 5 mg/L) or a ≥50% reduction from baseline values in patients with elevated biomarkers at study entry.

7. Change in Bowel Urgency Based on the Urgency NRS from Baseline to 12, 24 e 54 ± 4 weeks

 To evaluate changes in bowel urgency severity using the Urgency Numeric Rating Scale (NRS) at 12, 24 e 54 ± 4 weeks.

8. Comparing Effectiveness Across Different Treatment Lines by 54 ± 4 weeks

• To compare the efficacy of Etrasimod in achieving the primary study endpoint when used as a second, third, or fourth-line biological treatment.

9. Normalization of Bowel Wall Thickness (BWT) at 12, 24 e 54 ± 4 weeks (optional)

• To determine the proportion of patients exhibiting normalization of bowel wall thickness (BWT) on intestinal ultrasound (IUS), defined as a rectum ≤4.0 mm, sigmoid colon ≤4.0 mm, descending colon ≤3.0 mm, transverse colon ≤3.0 mm, and ascending colon ≤3.0 mm, at 12, 24 e 54 ± 4 weeks. This will be evaluated only in patients with increased BWT at baseline. [7,8]

10. Ultrasound Remission at 12, 24 e 54 ± 4 weeks (optional)

 To evaluate the proportion of patients achieving an intestinal ultrasound remission score of ≤6.2 based on the Milano Ultrasound Criteria (MUC) after 12, 24 e 54 ± 4 weeks of Etrasimod treatment. This will be evaluated only in patients with an MUC score >6.2 at baseline.

11. Deep Remission at 12, 24 e 54 ± 4 weeks

To assess the proportion of patients achieving deep remission at 12, 24 e 54 ± 4
weeks, defined as a rectal bleeding subscore of 0, a stool frequency subscore of 0,
and an eMayo score ≤1. [9]

12. Disease Clearance at 12, 24 e 54 ± 4 weeks

• To evaluate the proportion of patients achieving disease clearance at 12, 24 e 54 \pm 4 weeks, defined as simultaneous attainment of deep remission (see above) and histologic remission (Nancy Histological Index = 0, indicating absence of significant inflammatory infiltrate)

13. Quality of Life Assessment

- To assess changes in health-related quality of life, measured using the IBD Disability Index (IBD-Disk) and the Functional Assessment of Chronic Illness Therapy–Fatigue (FACIT–Fatigue) questionnaire, 12, 24 e 54 ± 4 weeks.
- 14. Safety assessment through the 54 weeks, reporting side effects related to Etrasimod

Study Population

Inclusion Criteria:

- Adults aged ≥18 years with a confirmed diagnosis of UC for at least 6 months.
- Moderate-to-severe UC defined by a Mayo Clinic total score between 6 and 12 inclusive, with an endoscopic subscore ≥2.
- Inadequate response, loss of response, or intolerance to at least one prior biologic therapy (e.g., anti-TNF agents, vedolizumab, ustekinumab).

Exclusion Criteria:

- Diagnosis of Crohn's disease or indeterminate colitis.
- History of colectomy or anticipated need for colectomy during the study period.
- Presence of colonic dysplasia or malignancy.
- Active or latent tuberculosis not adequately treated.
- Serious uncontrolled medical conditions (e.g., severe infection, significant hepatic or renal impairment).
- Known hypersensitivity to Etrasimod or its excipients.

Intervention

Etrasimod Dosing Regimen:

- Induction Phase:
 - Etrasimod 2 mg administered orally once daily.

Maintenance Phase:

• Etrasimod 2 mg administered orally once daily up to Week 54.

Study Assessments and Visits

Baseline (Week 0):

- Comprehensive clinical assessment, including 9-point MMS.
- Endoscopic evaluation to assess mucosal appearance (endoscopic MAYO and UCEIS scores).
- Histological assessment via biopsy (Nancy score).
- Baseline PROs, including urgency numeric scale (UNRS).
- Laboratory tests: FC, CRP, complete blood count (CBC), liver and renal function tests.
- Collection of demographic and disease-specific data.
- Ultrasound evaluation of colonic and rectal wall thickness, if feasible (Milan Ultrasound Criteria).

Week 12, 24, 54 Assessments:

- Clinical response and remission assessment.
- Laboratory tests: FC, CRP.
- PRO assessments, including UNRS.
- Endoscopic and histological evaluation at Week 54.
- Safety monitoring.
- Ultrasound evaluation (Week 54, if feasible).

Urgency Numeric Rating Scale (UNRS) Assessment:

- Urgency severity will be evaluated using the validated UNRS, with scores ranging from 0 (no urgency) to 10 (worst possible urgency).
- Improvement in UNRS scores will be analyzed at Weeks 12, 24, and 54, and correlated with clinical remission and mucosal healing.
- This assessment will provide insights into symptom control and quality of life improvements in Etrasimod-treated patients.

Safety Monitoring

- Adverse events will be recorded and graded according to the Common Terminology Criteria for Adverse Events (CTCAE) version 5.0.
- Immediate reporting of any serious adverse events to relevant regulatory bodies.

Sample Size Determination:

The required sample size for McNemar's test of paired proportions, based on the asymptotic approximation by Miettinen (1968), with a two-sided alpha level of 0.05, power of 0.8, probabilities of discordant pairs 0–1 and 1–0 equal to 0.35 and 0.10 respectively [10], and a drop-out rate of 5%, is 68 pairs. The McNemar test will be used to assess changes in paired proportions, particularly in the context of pre- and post-intervention comparisons of binary outcomes.

Data Collection

Statistical analysis

Continuous data will be expressed as mean ± standard deviation (SD) or median and interquartile range (25th-75th percentile), while categorical variables will be reported as absolute and relative frequencies. Normality will be assessed using the Kolmogorov-Smirnov test and Levene's test for homogeneity of variance. The primary endpoint is the proportion of patients achieving deep remission at Week 54, defined as a binary variable. To compare paired proportions (e.g., remission status at baseline vs Week 54), McNemar's test will be used. To identify predictors of remission, multivariable logistic regression models will be applied, adjusting for baseline covariates. Repeated measures at Weeks 12, 24, and 54 will be analyzed using generalized estimating equations (GEE) with an appropriate link function (logit for binary outcomes; identity for continuous) to account for within-subject correlations over time. When evaluating continuous outcomes, repeated-measures ANOVA or linear mixed models may be used as appropriate. Between-group comparisons of continuous variables will be conducted using Student's t-test or Mann-Whitney U test, depending on data distribution. Chi-square or Fisher's exact test will be used for categorical comparisons. Associations between variables will be assessed using Spearman's correlation coefficient. Survival outcomes (if any) will be analyzed using the Kaplan-Meier method, with comparisons made using the log-rank test. Hazard ratios (HR) will also be presented using smoothed estimates to visualize changes over time. A two-tailed p-value < 0.05 will be considered statistically significant. All analyses will be conducted using SPSS v27.0, R (version 3.4.3), and EZR.

Ethical Considerations

- The study will adhere to the Declaration of Helsinki and Good Clinical Practice (GCP) guidelines.
- Written informed consent will be obtained from all participants before any studyrelated procedures.

Enrollment Period

 Duration: Enrollment is planned to commence in July 2025 or upon commercial availability of the investigational drug, which is currently accessible exclusively under compassionate use. The enrollment window will extend for 6 months from the date of drug availability. Each participant will be followed for 54 ± 4 weeks from the time of inclusion.

Recruitment Strategy:

- Patients will be recruited from multiple specialized inflammatory bowel disease (IBD) centers across different geographic regions.
- Investigators will work closely with referring clinicians to ensure eligible patients are identified promptly.
- Digital outreach and patient registries may be utilized to enhance recruitment efforts.

Enrollment Monitoring:

- Monthly updates on enrollment numbers will be provided to participating centers.
- Interim analyses may be conducted to evaluate the recruitment pace and adjust strategies accordingly.

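### Clinical response at Weeks 12, 24 and 54 has two incompatible definitions, one on the total Mayo score and one on the 9-point modified Mayo score, and neither contains the other

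*Protocol*

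**What the plan says.** The Protocol defines clinical response in two places.

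- **Endpoints, Secondary Endpoints.** The item opens "Proportion of patients achieving clinical response at Weeks 12, 24, and 54, defined as" and continues with a "decrease from baseline in Mayo Clinic total score of ≥3 points and ≥30" percent, plus a rectal bleeding condition (a fall of at least 1, or an absolute subscore of 0 or 1).
- **Outcomes measurement, Secondary Outcome Measures, item 5.** Under the title "Clinical Response at 12, 24 and 54 ± 4 weeks", response is "defined as a decrease of at least 2 points and 30% from baseline in the 9-point MMS". The bleeding condition that goes with it has the same content as in the other place.

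Three other places bear on the point.

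- The inclusion criteria use the total score: "Moderate-to-severe UC defined by a Mayo Clinic total score between 6 and 12 inclusive, with an endoscopic subscore ≥2".
- The baseline visit lists "Comprehensive clinical assessment, including 9-point MMS". The list for Weeks 12, 24 and 54 asks for assessment of clinical response and remission without naming a score, and places endoscopy and histology at Week 54.
- Clinical remission, the first Primary Outcome Measure, is defined on the modified Mayo score.

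**The concern.** The outcome name, the weeks and the bleeding condition are the same in both places, but the scale and the threshold differ. Both entries are secondary, and no sentence ranks them or presents them as two endpoints. If one rule were simply stricter, the choice would move the response rate in a known direction. It is not, so the reported rate depends on which section the analyst follows, and the direction of the difference cannot be told in advance. The study is open-label and describes no control arm, so the response rate is itself the result. A definition left open until the data are in can be chosen with the rate in view.

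**Working it through.** The Protocol states no figure to reproduce here, so the check applies both rules to the same patients.

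**Inputs from the Protocol**
- Rule A (Secondary Endpoints): total Mayo falls by at least 3 points and at least 30%.
- Rule B (Secondary Outcome Measures, item 5): the 9-point MMS falls by at least 2 points and at least 30%.
- Both rules: rectal bleeding falls by at least 1, or is 0 or 1 at follow-up.
- Eligible baseline: total Mayo 6 to 12, endoscopic subscore 2 or 3.

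**Assumption.** Each item is scored 0 to 3. MMS is rectal bleeding + stool frequency + endoscopy (maximum 9). Total Mayo is MMS plus one further item (maximum 12). The Protocol does not list the components of the total score, but this fits its 9-point MMS and its upper limit of 12.

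**Worked examples** (bleeding condition met in both)

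| | MMS | Fourth item | Total Mayo | Rule A | Rule B |
|---|---|---|---|---|---|
| 1 | 6 to 4: fall 2, 2/6 = 33% | 2 to 2 | 8 to 6: fall 2, 2/8 = 25% | no | yes |
| 2 | 8 to 6: fall 2, 2/8 = 25% | 2 to 1 | 10 to 7: fall 3, 3/10 = 30% | yes | no |

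Example 1 fails Rule A on both its points and its percentage. Example 2 fails Rule B on percentage alone. Neither rule therefore contains the other.

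**Enumeration.** There are 98 eligible baseline combinations and 4 × 4 × 4 × 4 = 256 follow-up combinations, which gives 98 × 256 = 25,088 transitions. Both rules were applied to each.

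| Transitions | Both respond | Neither responds | Total Mayo only | MMS only | Discordant |
|---|---|---|---|---|---|
| No item worsens: 6,636 | 4,193 | 1,904 | 317 | 222 | 539 (539/6,636 = 8.1%) |
| All: 25,088 | 6,671 | 15,218 | 914 | 2,285 | 3,199 (3,199/25,088 = 12.8%) |

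Among non-worsening transitions with an MMS fall of exactly 2 points, 352 of 1,192 (about 30%) are discordant. Every pattern has equal weight, so these figures show where the rules part and do not predict patient proportions.

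**Timing.** On the stated composition, both scores contain the endoscopic subscore. Study Assessments and Visits schedules follow-up endoscopy only at Week 54. Neither rule can therefore be computed as written at Weeks 12 and 24. This is a separate problem, and choosing between the rules does not solve it.

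**The case against.** Most score patterns are classified alike by both rules, the outcome is secondary, and an analysis plan not shown here could say which rule governs. All of this is fair and limits the weight of the point. It does not remove the contradiction, because the Protocol already states two rules and a later plan would have to override one of them.

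Three stronger readings are tempting, and the Protocol does not support them.

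- *The total-Mayo rule cannot be computed because only MMS is collected.* Eligibility requires a total Mayo score, so its items must be available at baseline. The baseline line says that the assessment includes MMS, which is not an exhaustive list. The follow-up list names no score, so it favours neither rule. What stands is that the Protocol does not expressly require all items of the total score at follow-up.
- *Every patient with a 2-point MMS fall is in dispute.* Many agree. MMS 6 to 4 with the fourth item going from 2 to 1 gives total 8 to 5 (3/8 = 37.5%), a response on both. MMS 8 to 6 with the fourth item unchanged at 2 gives total 10 to 8, a non-response on both. Nor is disagreement confined to 2-point falls. MMS 9 to 6 (33%) with the fourth item unchanged at 3 gives total 12 to 9 (25%), a response on MMS only if bleeding qualifies.
- *About 8% of patients will be reclassified.* The figure counts possible patterns. The Protocol gives no distribution of scores from which a patient proportion could be derived.

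**Conclusion.** The point holds as an internal contradiction. One named secondary outcome has two rules for the same weeks, and they disagree in both directions. Under the stated composition of the scores, 8.1% of non-worsening eligible patterns are discordant (12.8% of all patterns). The effect on the reported response rate cannot be quantified from the Protocol. That the two rules conflict is plain from the text; the examples and counts rest on the assumption that total Mayo is MMS plus one further 0 to 3 item. The definition of deep remission and the sample size are untouched. It should be corrected, but it does not threaten the study's main result.

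**What to change.** Before data are seen, name one definition as the clinical response endpoint and use it in both Secondary Endpoints and Secondary Outcome Measures, item 5. The MMS version is the natural choice: it is the score named at the baseline visit and the one used for clinical remission. If response on total Mayo is also wanted, give it its own label and state that all items of the total score are recorded at follow-up. Either route is a short wording amendment.

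The Weeks 12 and 24 problem needs its own decision and is more than a one-line edit. Restricting the endpoint to Week 54 would mean aligning the secondary objective, the secondary endpoint, item 5 and the visit list, and checking the planned repeated-measures analysis at Weeks 12, 24 and 54. The loss would be modest, because symptomatic remission (Secondary Outcome Measures, item 3) needs no endoscopy and already covers Weeks 12 and 24.

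### Two different endpoints are called primary: deep remission at Week 54 in the objective and statistics section, clinical remission in the outcome list

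*Protocol*

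**What the plan says.** All references are to the protocol.

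- **Objectives, Primary Objective:** "Evaluate the effectiveness of Etrasimod in achieving deep remission at Week 54", with deep remission "defined as the simultaneous presence of clinical and endoscopic remission". No component scores are given.
- **Endpoints, Composite Endpoint:** "Proportion of patients achieving deep remission at 54 ± 4 weeks", scored as rectal bleeding 0, stool frequency 0 and endoscopic subscore 1 or less. Nothing under this heading carries the label primary.
- **Outcomes measurement, Primary Outcome Measures:** the single item is "Clinical Remission at 24 and 54 ± 4 weeks". The text under it names one time point only: "To assess the proportion of patients achieving clinical remission at 54 ± 4 weeks". It requires rectal bleeding 0, "stool frequency subscore of 0 or 1 with at least a 1-point reduction from baseline", and an endoscopic subscore of 0 or 1 without friability.
- **Outcomes measurement, Secondary Outcome Measures, item 11:** "Deep Remission at 12, 24 e 54 ± 4 weeks", with the same component scores as the composite endpoint.
- **Statistical analysis:** "The primary endpoint is the proportion of patients achieving deep remission at Week 54, defined as a binary variable".

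Secondary item 8 compares treatment lines on the primary study endpoint without saying which endpoint that is. No section ranks the two endpoints, calls them co-primary or divides alpha between them.

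**The concern.** One endpoint is primary in two sections and secondary in a third, while another endpoint holds the primary place in the formal outcome list. This is not detail left for a later analysis plan: the protocol states rules that conflict.

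The study is open-label and no comparator is described, so the Week 54 remission proportion is the main result. If two definitions can each claim to be primary, that proportion is not fixed in advance, and the text leaves room for the choice to be made once the data are known. Secondary item 8 inherits the same uncertainty.

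**Working it through.** **1. Does the plan's own figure settle the matter?** Sample Size Determination states 68 pairs for McNemar's test by the Miettinen approximation: two-sided alpha 0.05, power 0.80, discordant probabilities 0.35 and 0.10, drop-out 5%. With ψ = 0.35 + 0.10 = 0.45 and δ = 0.35 − 0.10 = 0.25:

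n = [z(1−α/2)·ψ + z(power)·√(ψ² − δ²(3+ψ)/4)]² / (ψδ²) = [1.960 × 0.45 + 0.842 × √(0.2025 − 0.0539)]² / 0.0281 = 51.7

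That is 52 pairs, and 52/0.95 gives 55 after drop-out. The stated 68 is not reproduced by the named method, which is a separate matter. What counts here is that the paragraph names no endpoint, so neither its inputs nor its total shows which endpoint is primary.

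**2. The definitions side by side**

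| Component | Deep remission (Endpoints; secondary item 11) | Clinical remission (Primary Outcome Measures) |
|---|---|---|
| Rectal bleeding | 0 | 0 |
| Stool frequency | 0 | 0 or 1, with a fall of at least 1 point |
| Endoscopic subscore | 1 or less, friability not mentioned | 0 or 1, friability excluded |
| Time point | Week 54 (item 11 adds Weeks 12 and 24) | Weeks 24 and 54 in the heading, Week 54 in the text |

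**3. Who is classified differently at Week 54**

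- Stool frequency falls from 2 to 1 and all else is in remission: clinical but not deep remission. This holds on any reading.
- Stool frequency 0 and an endoscopic subscore of 1 scored with friability: deep but not clinical remission. This holds only if deep remission does not tacitly share the friability exclusion.
- Stool frequency 0 at entry and at Week 54: deep remission is possible. Clinical remission is ruled out if the 1-point fall applies to both scores, but not if it applies only to a score of 1. Assuming the usual four-component Mayo score, such a patient can be eligible: 0 + 2 + 2 + 2 = 6, with endoscopic subscore 2.

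**4. The objective's wording.** The protocol's clinical remission already includes endoscopy and allows stool frequency 1. Its symptomatic remission (secondary item 3) also allows stool frequency 1. On either reading of the word clinical, the objective's description of deep remission admits patients whom the composite endpoint excludes.

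**5. Effect on the proportion.** Let a be the share in clinical but not deep remission, and b the share in deep but not clinical remission. The clinical remission proportion exceeds the deep remission proportion by a − b. The documents give neither quantity. With 68 × 0.95 = 64.6, taken as 64 evaluable patients, each net patient moves the result by 1/64 = 1.6 points.

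**6. Effect on the test.** Entry requires an endoscopic subscore of at least 2 and both endpoints require 1 or less, so no eligible patient is in either state at baseline. The cell for losing remission is therefore empty, and the exact two-sided McNemar p-value with k remitters is 2 × 0.5^k: 0.0625 for k = 5 and 0.031 for k = 6. Six remitters of 64 (9.4%) are enough under either definition. Switching endpoints changes significance only if one yields fewer than six remitters and the other six or more.

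**7. Week 24.** Clinical remission needs an endoscopic subscore. Study Assessments and Visits schedules post-baseline endoscopy at Week 54 only, so the Week 24 version cannot be assessed as defined.

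**The case against.** The strongest reply is that the protocol does answer the question. The primary objective names deep remission at Week 54, the statistics section calls it the primary endpoint outright, and the composite endpoint supplies its scores. Only the outcome list departs from this, and an analysis plan that is not shown may settle it. The objective's wording can also be read as a loose summary of the composite rather than a rival definition. Much of this stands: it makes deep remission the natural choice. It does not remove the conflict, because the outcome list is explicit about what is primary and separately lists deep remission as secondary.

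Four stronger readings are tempting, and the documents do not support them.

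- *There is no primary hypothesis, or the endpoint is meant to be picked afterwards.* Two sections agree on deep remission. A late choice is a risk left open, not a stated intention.
- *The type I error rises to 0.14.* The figure 1 − 0.95³ = 0.143 assumes three independent tests. One is the Week 24 endpoint that cannot be assessed, and the two Week 54 endpoints share components in the same patients. Even two independent tests give at most 1 − 0.95² = 0.0975, and step 6 shows that the test hardly separates the endpoints.
- *The remission rate shifts by 10 to 20 points.* That would be an assumption about a − b with no source in the documents, and patients in group b would offset those in group a.
- *The total of 68 implies alpha was split over two primary endpoints.* The formula at alpha 0.025 does give 63.2, so 64, and 64/0.95 gives 68. But the protocol states alpha 0.05 and mentions no split, so the match is no evidence of one.

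**Conclusion.** The point holds. The protocol calls two different endpoints primary and also lists one of them as secondary. The secure difference between them is stool frequency 1 after a fall of at least one point. The friability difference and the case of stool frequency 0 at entry depend on how unclear wording is read.

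The harm is to the reported Week 54 remission proportion and to secondary item 8, not to the McNemar p-value. Its size cannot be derived from the documents beyond 1.6 points per net reclassified patient, assuming 64 evaluable patients. The contradiction should be removed before outcome data are examined.

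**What to change.** Amend the wording as follows.

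1. Make deep remission at Week 54 the only primary endpoint: rectal bleeding 0, stool frequency 0, endoscopic subscore 1 or less. State once whether friability is excluded.
2. Use that component definition in Objectives, Endpoints, Outcomes measurement and Statistical analysis.
3. Move clinical remission at Week 54 to the secondary measures, and say whether the 1-point fall applies to stool frequency 0 or only to 1.
4. Delete Week 24 from clinical remission, since no endoscopy is scheduled then.
5. Remove Week 54 from secondary item 11. The Weeks 12 and 24 that remain there meet the same endoscopy gap and must be reconciled with the visit schedule.
6. Name the primary endpoint in Sample Size Determination and in secondary item 8.

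The cost is a wording amendment. It needs no new data, visits or patients.

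### Clinical response at Weeks 12 and 24 is defined on scores that contain the endoscopic subscore, but the visit list places post-baseline endoscopy at Week 54 only, so the result depends on an unstated handling rule

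*Protocol*

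**What the plan says.** All references are to the Protocol.

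- **Outcomes measurement, secondary item 5**, is headed "Clinical Response at 12, 24 and 54 ± 4 weeks". Response is "defined as a decrease of at least 2 points and 30% from baseline in the 9-point MMS". A bleeding condition is added: the bleeding subscore must drop by a point or more, or stand at 0 or 1 when the patient is assessed.
- **Endpoints, Secondary Endpoints**, has a second definition for the same visits, on another score: "a decrease from baseline in Mayo Clinic total score of ≥3 points and ≥30" per cent, plus a similar bleeding condition.
- **Study Assessments and Visits**, in the list for Weeks 12, 24 and 54, has "Endoscopic and histological evaluation at Week 54". The objectives also place mucosal and histological healing at Week 54.
- **Inclusion Criteria** require a "Mayo Clinic total score between 6 and 12 inclusive, with an endoscopic subscore ≥2".
- The modified Mayo score (MMS) is described under primary outcome 1 by its bleeding, stool frequency and endoscopic subscores. The full 9-point MMS is taken at baseline.
- No partial score is named for response at Weeks 12 and 24, and no rule is given for the absent endoscopic item. Item 3 (symptomatic remission) uses bleeding and stool only, but response has no such counterpart.

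**The concern.** This is not sporadic missing data. On the visit list, the endoscopic item is absent for every patient at two of the three visits where response is to be reported.

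A rule based on a fall from baseline is sensitive to this. Every patient enters with an endoscopic subscore of 2 or 3, so a program that sums whatever items are present would record a fall of 2 or 3 points before any symptom changed. Other ways of filling the gap give quite different answers, and some make response unattainable for certain patients. The study is open-label and describes no control group, so no comparator would expose an artefact. A change in score content between Week 24 and Week 54 could also look like a time trend.

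**Working it through.** The plan states no figure to reproduce. The check applies the response rule to every baseline that the entry criteria allow.

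**Inputs.** Bleeding (RB) 0–3, stool frequency (SF) 0–3, endoscopic subscore (ES) 2 or 3, physician global assessment (PGA) 0–3, total 6–12. The 0–3 range per item is an assumption, consistent with a 9-point three-item score and a 12-point total.

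**Eligible baselines.** RB × SF × ES gives 4 × 4 × 2 = 32 MMS profiles. Only RB 0, SF 0, ES 2 cannot reach a total of 6 (at most 2 + 3 = 5), leaving 31. With PGA there are 98 four-item combinations: 44 with ES 2 and 54 with ES 3.

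**Rule (item 5).** Fall ≥2 points, fall ÷ baseline ≥30%, and RB down by ≥1 or RB at the visit ≤1.

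**A. ES in the baseline, left out at the visit; symptoms unchanged.** The fall equals baseline ES, so the 2-point condition is always met.
- RB 0 or 1 (7 + 8 = 15 profiles): the smallest percentage fall is at RB 1, SF 3, ES 2, from 6 to 4, or 2/6 = 33.3%. All 15 respond.
- RB 2 or 3 (16 profiles): the bleeding condition fails, so none respond unchanged. All 16 respond after a 1-point fall in bleeding alone.
- In 6 profiles (ES 3, RB ≤1, SF ≤2), response is still recorded when SF worsens by 1 point.

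**B. Baseline ES carried forward.** The fall can come only from RB + SF. With symptoms unchanged, 0 of 31 respond. With RB and SF both falling to 0, the fall is RB + SF, which is below 2 in 5 profiles (RB/SF/ES = 0/0/3, 0/1/2, 0/1/3, 1/0/2, 1/0/3). These can never respond.

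**C. ES dropped at both times, 2-point and 30% rules applied to RB + SF.** With symptoms unchanged, 0 of 31 respond. The same 5 profiles cannot respond.

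**D. Score treated as missing.** No patient is evaluable, or none responds if missing counts as non-response.

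| Handling | Respond, symptoms unchanged | Cannot respond even at RB = SF = 0 | Responding pairs of baseline profile and visit RB/SF (31 × 16 = 496) |
|---|---|---|---|
| A | 15 of 31 | 0 of 31 | 237 |
| B | 0 of 31 | 5 of 31 | 95 |
| C | 0 of 31 | 5 of 31 | 116 |

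**Mayo total version, handling A, PGA unchanged.** With ES 2 the fall is 2, below the 3-point minimum, so 0 of 44 respond. With ES 3 and RB ≤1 the total is at most 1 + 3 + 3 + 3 = 10, so the fall is at least 3/10 = 30%. There are 10 (RB 0, SF + PGA ≥3) + 13 (RB 1, SF + PGA ≥2) = 23 such combinations, and all respond: 23 of 98.

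**Threshold for a two-item symptom score (0–6).** With 30% alone, a 1-point fall can qualify when the baseline sum is 1, 2 or 3, which is 4 + 6 + 8 = 18 of 31 profiles. With the 2-point minimum kept, sums of 0 or 1 cannot respond: 1 + 4 = 5 of 31. A sum of 0 (1 profile) has no percentage fall.

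**The case against.** **The automatic responders are hypothetical.** This stands. A reader might infer that, because every patient enters with ES ≥2, the Week 12 and 24 rates will be inflated. The documents do not support that. It needs the item dropped at the visit but kept in the baseline, which the Protocol does not prescribe. It also needs baseline bleeding of 0 or 1, and on the Mayo total version ES 3 as well.

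**The visit list may be the wrong side of the contradiction.** This also stands. Deep remission and disease clearance (items 11 and 12) are set at 12, 24 and 54 weeks and need endoscopy, the latter histology too. The list looks incomplete elsewhere: it gives ultrasound at Week 54 only, although items 9 and 10 want it at 12 and 24 weeks, and it does not name the quality-of-life questionnaires. One cannot conclude that endoscopy will not be done at the earlier visits, only that the sections disagree.

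**Scoring of missing items belongs in the SAP, which is not shown.** This holds for occasional gaps. Here the definition and the schedule conflict for every patient, and the Protocol itself fixes both.

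**The consequence is limited.** Largely true. This is a secondary outcome at two interim visits, deep remission at Week 54 is unaffected, and item 3 already gives an endoscopy-free outcome. A reader might also take any GEE trend to be an artefact, but the Statistical analysis section does not name clinical response as a GEE outcome.

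**Conclusion.** The point holds as a contradiction between the response definitions and the visit schedule. As written, clinical response cannot be computed at Weeks 12 and 24, and the reported rate would depend on an unstated choice. With symptoms unchanged, that choice moves the number of responding profiles from 0 to 15 of 31 on the MMS, and from 0 to 23 of 98 on the Mayo total score when the item is left out at the visit only.

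These figures assume 0–3 per item and, for the total score, an unchanged PGA. They weight all profiles equally and are not patient rates: the Protocol gives no baseline distribution of bleeding or stool scores, so the size of any bias in patients cannot be stated.

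The same mismatch affects clinical remission at Week 24 (in the heading of primary outcome 1, although its text names only 54 weeks) and deep remission and disease clearance at Weeks 12 and 24. It is best corrected once for all of them, before data are scored.

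**What to change.** 1. Reconcile the outcome timings with the visit list, for response and for the remission and clearance outcomes together, and keep one of the two response definitions.
2. If endoscopy stays at Week 54 only, report MMS clinical response at Week 54 only. At Weeks 12 and 24 report a separately named symptomatic response on bleeding plus stool frequency (0–6), with baseline and visit scored on the same items.
3. State its threshold in advance, including whether the 2-point minimum is kept. Either choice has the cost shown above: 18 of 31 profiles can qualify on a 1-point fall, or 5 of 31 cannot respond. Say how a baseline sum of 0 is handled.
4. Use the symptom version at all three visits for any longitudinal (GEE) analysis, and do not mix the two scores in one model.

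If endoscopy stays at Week 54 only, the cost is a wording change with no new procedure. The downside is that the early measure differs in name and scale from the Week 54 one and is not directly comparable with MMS response.
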